9.3.2 Pharmacokinetic Statistical Methodology

For all cohorts, log-transformed C_{max} , AUC(0-24), AUC(0- t_{last}) (Day 3 only), and AUC(0- ∞) (Day 3 only) parameters of LY3493269 on Days 1 (first dose) and 3 (third dose) independently will be evaluated using a power model (where log-dose acts as an explanatory variable, and SNAC fitted as a dichotomous variable in which the variable equals 0 for those doses with 300 mg SNAC, and 1 for those with 600 mg SNAC) to estimate ratios of dose-normalized geometric means and corresponding 90% confidence intervals (CIs). The estimated ratio of dose-normalized geometric means of PK parameters between the highest and lowest doses will be used to assess dose proportionality. The 90% CI will also be reported for the parameter of the SNAC variable. A subinterval within the highest and lowest doses may also be considered for assessment of dose proportionality using the same approach.

Example of the SAS code (for C_{max} and $AUC[0-24]$) for the analysis:

```
proc mixed data=xxx;
  class usubjid SNAC;
  model log_pk = log_dose SNAC / alpha=0.1 cl solution outpred=resids ddfm=kr;
  estimate 'xx mg' intercept 1 log_dose yy / alpha=0.1 cl; /*Log value of xx*/
  estimate 'zz mg - xx mg' log_dose pp / alpha=0.1 cl; /*Difference in log
values of zz and xx*/
  ods output solutionf=est;
  ods output estimates=estims;
run;
```

The LY3493269 parameter t_{max} will be analyzed non-parametrically using the Kruskal-Wallis test to investigate its independence, and, hence, dose proportionality, with the respective p-value reported. For each dose, 90% CIs for the median will also be reported.

Example SAS code is as follows:

```
proc nparlway data=xxx
  class dose;
  var pk;
  ods output KruskalWallisTest=krusk;
run;
```

For Cohorts 1 and 2, and 3 and 4 independently, log-transformed dose normalized C_{max} , $AUC(0-24)$, $AUC(0-t_{last})$ (Day 3 only), and $AUC(0-\infty)$ (Day 3 only) parameters of LY3493269 on Days 1 (first dose) and 3 (third dose) will be analyzed independently an analysis of variance model to assess dose proportionality. The model will include treatment as a fixed effect. The difference in least-square (LS) treatment means and respective LS means will be back transformed to produce the ratio of geometric means, and the 90% CIs of the LS means and difference between the means will be reported.

Example of the SAS code for the dose normalized analysis:

```
proc mixed data=xxx;
  class usubjid;
  model log_DNpk = treatment / alpha=0.1 cl solution outpred=resids ddfm=kr;
  ods output lsmeans=lsm diffs=estims;
run;
```

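### The example SAS code in SAP 9.3.2 does not return the dose-normalized ratio, the SNAC direction or the LS means that the text specifies

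*SAP*

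**What the plan says.** SAP 9.3.2 specifies two analyses of LY3493269 Cmax and AUC, for Days 1 and 3 separately.

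**Power model, all cohorts.** Log PK is regressed on log dose plus a SNAC indicator, for which "the variable equals 0 for those doses with 300 mg SNAC, and 1 for those with 600 mg SNAC". The criterion is explicit: "The estimated ratio of dose-normalized geometric means of PK parameters between the highest and lowest doses will be used to assess dose proportionality". The text adds: "The 90% CI will also be reported for the parameter of the SNAC variable". The example code fits `log_pk`, lists SNAC in CLASS and in MODEL, and has two ESTIMATE rows: "estimate 'xx mg' intercept 1 log_dose yy / alpha=0.1 cl" and "estimate 'zz mg - xx mg' log_dose pp / alpha=0.1 cl". A comment in the code defines `pp` as the difference in log doses.

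**Dose-normalized ANOVA, Cohorts 1 and 2 and Cohorts 3 and 4 separately.** The text asks for LS means and their difference, back-transformed, with 90% CIs. The model line is "model log_DNpk = treatment / alpha=0.1 cl solution outpred=resids ddfm=kr". CLASS lists only the participant identifier. The output line requests the LS-means and differences tables, but the block has no LSMEANS statement.

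**The concern.** Text and code disagree on scale and direction in the only model-based analyses that the SAP specifies for the secondary endpoints, AUC and Cmax. SAP Section 3 says that the SAP supersedes the protocol's statistical section and, with the table shells, serves as the template for the study report.

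Two of the mismatches give plausible numbers rather than a failure. A ratio on the raw scale has its proportionality value at the dose ratio, not at 1. A SNAC effect with the reverse sign would point the wrong way on whether 300 mg SNAC gives bioavailability comparable to 600 mg, which is the stated purpose of Cohort 4 in Protocol 4.3. The ANOVA mismatch means that the promised output is absent.

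**Working it through.** The documents give no numerical result here, so there is no figure to reproduce. The check compares what each line of code estimates with what the text names.

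**Inputs.** From SAP Section 5: 8, 24 and 48 mg with 600 mg SNAC, and 24 mg with 300 mg SNAC; 8 active participants per cohort. From the SAP Section 6 table: 8 and 24 mg with 600 mg, 12 and 4 mg with 300 mg. The highest/lowest dose ratio is r = 48/8 = 6 under the first list and 24/4 = 6 under the second. Assumed, not from the documents: the values of β, the SNAC effects, the residual SD and the power-model intercept of 1 used below, and default SAS ordering of CLASS levels (last level as reference).

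**1. High/low ratio.** The model is ln(PK) = α + β·ln(dose) + SNAC effect. The contrast `log_dose pp`, with pp = ln(r), estimates β·ln(r), which back-transforms to r^β. The dose-normalized ratio is r^β / r = r^(β − 1). With r = 6:

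| β | Code, 6^β | Text, 6^(β − 1) |
|---|---|---|
| 0.8 | 4.19 | 0.70 |
| 0.9 | 5.02 | 0.84 |
| 1.0 | 6.00 | 1.00 |
| 1.1 | 7.18 | 1.20 |
| 1.2 | 8.59 | 1.43 |

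Dividing the estimate and both CI limits by 6 converts one scale to the other exactly. In one simulated data set (Section 5 list, β = 1, log SNAC effect +0.30, residual SD 0.6) the code's ratio was 5.68 (90% CI 3.74 to 8.64). Divided by 6, this is 0.947 (0.623 to 1.44).

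**2. SNAC parameter.** The text's coding makes the parameter the 600-minus-300 difference on the log scale. With SNAC in CLASS and level 1 (600 mg) as reference, the printed row is 300 minus 600. A true effect of +0.30 (ratio 1.35) prints as −0.30 (ratio 0.74). A true 1.5-fold increase prints as −0.405 (ratio 0.67). The absolute size and the CI width do not change.

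**3. Dose-level row.** The design columns are intercept, log dose, SNAC = 300 and SNAC = 600. With 8 participants per cohort the rank is 3 of 4, under either regimen list.
- If the omitted SNAC coefficients are zero, the row (1, yy, 0, 0) is outside the row space, so it is not estimable.
- If the software spreads the intercept equally over the SNAC levels, the row (1, yy, 0.5, 0.5) is estimable but averages over 300 and 600 mg. In a noise-free example at 8 mg (intercept 1, β = 1, SNAC effect +0.30) it gives 25.3, against 29.4 at 600 mg and 21.7 at 300 mg.
- With an explicit level, (1, yy, 0, 1), it is estimable and is the mean at 600 mg SNAC.

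**4. ANOVA block.** Treatment is the only model effect but is not in CLASS, and nothing in the block generates the two tables that the output line requests. The PD block in SAP 9.4.2 and the vital-signs block in SAP 9.6.5 both have treatment in CLASS and an LSMEANS statement, so the omission is not the SAP's usual shorthand.

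**The case against.** The best defence is that both blocks are labelled as examples and contain placeholders, and that the prose sets the estimands. The contrast is labelled as a difference between two doses and is correct as such. The code exports its estimates without exponentiating them, so some post-processing is presupposed. The SNAC issue is a choice of reference level. A missing LS-means table would be noticed at once. The endpoints are secondary and the study is not powered for hypothesis tests. All of this stands as a limit on severity. It does not remove the mismatch: the SAP names a dose-normalized ratio and a coded SNAC direction, and states neither the conversion nor the reference level. The table shells mentioned in SAP Section 3 are not among the documents, so they cannot be relied on to fill the gap.

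A reader might infer more than the documents support:
- That every dose-level row will print as non-estimable. This depends on how omitted CLASS coefficients are filled, which the documents do not settle. The ECG code in SAP 9.6.6 also leaves a CLASS effect (time) out of its ESTIMATE rows, which is consistent with relying on automatic fill-in but does not prove it.
- That promised dose-level means are lost. The power-model text does not promise them; only the code's row produces them. SAP 9.1 provides descriptive geometric means in any case.
- That SAP version 3 added SNAC and left the old ESTIMATE rows in place. The document history says that the analysis was extended to all doses and that the dose-normalized analysis was added, but the earlier code is not available. This origin is an inference only.

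**Conclusion.** Wrong as written, minor to moderate. Run as shown, the power-model contrast gives the raw ratio, which exceeds the dose-normalized ratio by the dose ratio, 6 under either regimen list. Under default CLASS ordering the SNAC parameter has the opposite sign to the text. The dose-level row does not give the mean of a studied regimen, whichever way the omitted coefficients are handled. The ANOVA block does not yield the LS means and differences that the text asks for.

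It does not follow that the reported assessment of proportionality would be wrong. The contrast is right for its own label, and an exact conversion exists; what is missing is the statement of that step. The first and fourth findings follow from algebra and from the code as printed. The second rests on default level ordering, and the third holds under both ways of filling the coefficients.

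**What to change.** In SAP 9.3.2:

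- **Scale.** Either fit log(PK/dose), so that the log-dose slope is β − 1 and the contrast is already dose-normalized, or keep `log_pk` and state that ln(zz/xx) is subtracted from the contrast and both CI limits before exponentiating. Under the first option any dose-level row becomes a dose-normalized mean and should be labelled so.
- **SNAC.** Enter it as a numeric 0/1 covariate outside CLASS, or state the reference level, and report the exponentiated parameter as the 600/300 ratio with its 90% CI.
- **Dose-level rows.** Give each one the SNAC level of its regimen (with numeric coding, `SNAC 1` for 600 mg and `SNAC 0` for 300 mg). Taking SNAC out of CLASS without this coefficient would place every mean at 300 mg SNAC. The Cohort 3 and 4 regimens differ between SAP Sections 5 and 6 and must be reconciled first.
- **ANOVA.** Use `class treatment;` and add `lsmeans treatment / cl pdiff alpha=0.1;`.

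The cost is a few lines of SAP code. No data collection, sample size or endpoint changes.

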9.4 Pharmacodynamic Assessment

9.4.1 Pharmacodynamic Analysis

Pharmacodynamic data will be provided by Eli Lilly and Company for the analysis.

9.4.2 Pharmacodynamic Statistical Methodology

The PD parameters from the placebo-treated participants across all cohorts will be pooled for the final analysis.

All exploratory PD parameters, including the change from baseline parameters, will be summarized and listed by treatment group and visit. Individual observed and mean time profiles of the postdose PD parameters will be plotted by treatment groups.

The PD parameters that will be statistically analyzed, which have a baseline defined as Day 1 predose, are as follows:

- Fasting glucose
- Fasting insulin
- Fasting C-peptide
- Fasting triglycerides
- Body weight
- Appetite VAS

The PD parameters, as well as the change from baseline parameters, will be analyzed using a mixed effect model. In the model, treatment, visit, and treatment-by-visit interaction will be modelled as fixed effects; participants will be modelled as a random effect. Baseline will also be included as a covariate when the response involves change from baseline. An unstructured covariance structure will be used to model the covariance between a participant's multiple observations, with an alternative structure to be used if the model fails to converge, using a measure such as Akaike's information criterion to decide which structure will be used. If necessary, the response may be transformed before the analysis, with back-transforming to the original scale implemented for the results. For each PD parameter, the difference in LS treatment means, comparing LY3493269 (test) and placebo (reference), along with the 90% CI, will be reported.

Example of the SAS code to be used for the mixed effect model analysis:

```
proc mixed data=xxx;
class treat visit subject;
model PD = treat visit treat*visit /residual ddfm=kr;
repeated visit / subject=subject type=un;
lsmeans treat*visit / cl pdiff alpha=0.1;
ods output lsmeans=lsm diffs=estims;
run;
```

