9.2. Sample Size Determination

The sample size is customary for Phase 1 studies evaluating safety and PK and is not powered on the basis of statistical hypothesis testing.

Up to approximately 56 participants may be randomly assigned to study intervention to ensure approximately 10 evaluable participants (8 receiving LY3493269 and 2 receiving placebo) from each of the 4 cohorts complete the study. Participants who are randomized but not administered treatment prior to discontinuation may be replaced to ensure that the target number of participants complete the study.

Participants who discontinue early may be replaced after consultation with the investigator and sponsor. The replacement participant will be assigned to the same treatment as the discontinued participant.

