9.4.5. Pharmacodynamics Analyses

Inferences will be sought regarding the effect of LY3493269 on the PD endpoints. Such effects will be explored over different doses of LY3493269 and at applicable time points as per the SoA (Section 1.3).

Pharmacodynamic parameters may be transformed before statistical analyses, if deemed necessary. Absolute values, as well as change from baseline, in each parameter will be analyzed using mixed-effects models to evaluate treatment effects, as well as treatment comparisons. The model will include treatment, visit, and treatment-by-visit interaction as fixed effects and participant as a random effect. Baseline values, as well as other influencing variables, may be used as covariates. Differences between each LY3493269-treated group and placebo group will be estimated. Participants who received placebo will be pooled across all cohorts. Least squares means and 90% CIs will be reported.

All PD parameters, including the baseline-corrected parameters, will be summarized and tabulated by treatment group and visit. Summary statistics will be provided. The individual observed and mean time profile of the postdose PD parameters will be plotted by treatment group.

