9.6.5 Vital signs

Vital signs data will be summarized by treatment together with changes from baseline, where baseline is defined as the Day 1 predose assessment. Figures of mean vital signs and mean changes from baseline profiles will be presented by treatment.

Values for individual participants will be listed.

Changes from baseline values will be analyzed using a repeated measurement mixed effect model. The model will include treatment, timepoint, and treatment-by-timepoint interaction as fixed effects; participant will be included as a random effect. Baseline will also be included as a covariate in the model. An unstructured covariance structure will be used to model the covariance between a participant's multiple observations, with an alternative structure to be used if the model fails to converge, using a measure such as Akaike's information criterion to decide which structure will be used. The difference in least-square treatment means, comparing LY3493269 (test) and placebo (reference), along with the 90% CI, will be reported. Example SAS code for the analysis:

```
proc mixed data=xxx;
  class time treat subject;
  model change = treat time treat*time base /residual ddfm=kr;
  repeated day / subject=subject type=un;
  lsmeans treat*day / cl pdiff alpha=0.1;
  ods output lsmeans=lsm diffss=estims;
run;
```

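### SAP 9.4.2 compares absolute PD values with placebo without baseline adjustment, alongside the adjusted change contrasts: a less precise second result that is easily fixed

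*SAP*

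**What the plan says.** Protocol 9.4.5 puts both forms of each PD parameter into the model: "Absolute values, as well as change from baseline, in each parameter will be analyzed using mixed-effects models". It leaves adjustment open for either form: "Baseline values, as well as other influencing variables, may be used as covariates".

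SAP 9.4.2 keeps both responses: "The PD parameters, as well as the change from baseline parameters, will be analyzed using a mixed effect model". It then narrows the adjustment: "Baseline will also be included as a covariate when the response involves change from baseline". The six parameters are fasting glucose, insulin, C-peptide and triglycerides, body weight and appetite VAS, each with Day 1 predose as baseline. For each one, the treatment difference from pooled placebo is reported with a 90% CI. The response may be transformed if necessary.

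The section's one code example has this model line: "model PD = treat visit treat*visit /residual ddfm=kr". The vital-signs example in SAP 9.6.5 does carry the baseline: "model change = treat time treat*time base /residual ddfm=kr".

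The exploratory endpoints in Protocol section 3 and SAP 4.3 are changes from baseline for the four fasting markers and body weight, and change in VAS score for appetite.

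**The concern.** Read literally, the SAP yields two treatment differences per parameter and visit: one adjusted for baseline, one not. It does not say which takes precedence. In groups of 8, a chance difference at Day 1 passes into the unadjusted contrast in proportion to the correlation between baseline and later values. The unadjusted result is then less precise and may differ noticeably from the adjusted one.

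Two features make this more than a duplicate table. First, the code shows no baseline term for any PD response, so a programmer who reuses it for the change response would leave out the covariate that the text requires. Second, a raw change can be negative and cannot be log-transformed. If a skewed marker is analysed on the log scale, the natural response is the logged absolute value, which is the form the text leaves unadjusted.

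**Working it through.** **Plan figure.** The documents state no SD, effect size, correlation or power for PD, so there is no figure to reproduce. Every r and SD below is an assumption.

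**Inputs from the documents.**
- Group sizes, Protocol 9.2: "approximately 10 evaluable participants (8 receiving LY3493269 and 2 receiving placebo) from each of the 4 cohorts complete the study". Placebo is pooled in SAP 9.4.2, so each contrast is 8 against 4 × 2 = 8.
- The interval is a two-sided 90% CI (SAP 9.4.2).
- Entry BMI may run from 19.0 to 40.0 kg/m² (Protocol 5.1).

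**Formulas, in units of the between-participant SD at one visit.**
- Unadjusted SE = sqrt(1/8 + 1/8) = 0.500.
- Baseline-adjusted SE = 0.500 × sqrt(1 - r²).
- Ratio of interval widths = 1/sqrt(1 - r²).
- Share of the unadjusted contrast's variance due to baseline imbalance = r².
- Power for an illustrative 0.8 SD effect, by normal approximation with 1.645. Unadjusted: Φ(0.8/0.500 - 1.645) = 48%.

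| Assumed r | Adjusted SE | Width ratio | Baseline share | Power, adjusted |
|---|---|---|---|---|
| 0.3 | 0.477 | 1.05 | 9% | 51% |
| 0.5 | 0.433 | 1.15 | 25% | 58% |
| 0.7 | 0.357 | 1.40 | 49% | 72% |
| 0.9 | 0.218 | 2.29 | 81% | 98% |
| 0.95 | 0.156 | 3.20 | 90% | about 100% |

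The baseline share passes one half at r = sqrt(0.5) = 0.71.

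**Chance imbalance.** The baseline mean difference also has SE 0.5 SD, so it exceeds 0.5 SD in either direction with probability 2 × (1 - Φ(1)) = 32%.

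**Simulation.** This used 10,000 trials for each r of 0.5, 0.7, 0.9 and 0.95, with 8 per group, one visit and no true effect.
- The mean unadjusted contrast was within 0.005 SD of zero, and the 90% CI covered 89.7% to 90.3%. The cost is precision, not bias or error rate.
- The empirical SD of the adjusted contrast was 0.450, 0.373 and 0.228 at r = 0.5, 0.7 and 0.9. This is slightly above the formula because the slope is estimated from 16 participants. The ratios of empirical SDs are 0.498/0.450 = 1.11, 0.501/0.373 = 1.34 and 0.502/0.228 = 2.20, so the tabulated ratios are slightly generous.
- With baseline as covariate, the absolute and change contrasts agreed to about 5 × 10⁻¹⁵. Algebraically, subtracting the baseline from the response lowers the baseline slope by 1 and leaves the treatment coefficient unchanged.

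**Body weight, as illustration.** With 35 degrees of freedom (40 participants, 5 groups) the unadjusted 90% half-width is 0.845 SD. At an assumed SD of 12 to 15 kg that is 10.1 to 12.7 kg. Dividing by 3.20 (r = 0.95) gives 3.2 to 4.0 kg; dividing by 7.09 (r = 0.99) gives 1.4 to 1.8 kg.

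**Baseline as a visit level.** SAP 9.4.2 does not say whether Day 1 predose is one of the visits in the absolute-value model. Keeping it there does not supply the adjustment: with a treatment-by-visit interaction, unstructured covariance and complete data, the later contrast is still the raw difference in means.

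**The case against.** The strongest reply is that the adjusted contrast is already planned. Every listed PD endpoint is a change from baseline, and the SAP text adjusts that response. This stands, and it limits the point to a redundant, less precise second contrast. It does not remove the point, because the absolute-value differences are reported with intervals and the SAP ranks neither result.

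The code can also be defended. It is labelled an example and its response is `PD`, for which the text asks for no baseline, so it matches the text for absolute values. That is right. What remains is that no PD example shows the covariate for the change response, whereas the vital-signs example does.

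Nor do these results drive decisions. The study is not powered for hypothesis tests, and Protocol 6.6.1 makes safety the primary criterion for escalation, with PD data as optional support. That also stands.

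Two stronger readings are tempting and are not supported:
- A reader might infer that the absolute-value contrasts mostly reflect chance baseline differences. That needs r above about 0.71, and the documents give no correlation. It is plausible for body weight over days to weeks, but only an assumption for the fasting markers and appetite.
- A reader might infer that the contrasts are biased or their intervals invalid. Under randomisation they are neither; the wider interval already expresses the imbalance.

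One caveat runs the other way. The simulation treats the 16 participants as one randomised set, whereas placebo is pooled over cohorts that are largely sequential and the model has no cohort term. Differences between cohorts at baseline could add to the imbalance, which favours adjustment.

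**Conclusion.** The point holds as a minor improvement. The absolute-value PD contrasts are unadjusted by the SAP's own rule, and the PD code shows no baseline term for either response. The consequence is intervals about 1.15, 1.40 and 2.29 times as wide as necessary at assumed r of 0.5, 0.7 and 0.9, with little lost at 0.3. The loss is probably greatest for body weight, given the wide BMI range. The body-weight figures in kilograms rest on assumed SDs and correlations and show scale only.

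The documents do not support saying that the PD endpoints lack baseline adjustment: the change analysis, which matches those endpoints, is adjusted in the text.

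**What to change.** In SAP 9.4.2:
1. Fit both models only to visits after Day 1 predose, so that the baseline measurement is not on both sides of the model.
2. Include the Day 1 predose value as a covariate in both, on the same scale as the response. If the response is logged, log the baseline too.
3. Add `base` to the PD MODEL statement.

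On a common scale the two treatment differences then coincide, so one needs reporting. They would not coincide if a logged absolute value were set beside a raw change.

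Alternatively, name the baseline-adjusted change contrast as the only inferential PD comparison and present absolute values descriptively. The code term for the change model is still needed.

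The cost is a sentence or two, one code term and one degree of freedom for the baseline slope. No new data are needed, since Day 1 predose is already scheduled for all six parameters, and Protocol 9.4.5 already permits the covariate for either response.
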